## 4.4 **Population PK Analyses**

PK data will be analyzed and reported separately. Details of the PK data summaries and analysis methods will be provided in a separate analysis plan.

## 4.5 Safety Analyses

The primary population for all safety analyses will be the Safety population. In safety analyses, treatment classification will be based on the actual treatment received. Unless otherwise specified, no formal statistical hypothesis testing will be performed for safety endpoints, and the presentations will be based on descriptive summaries.

The impact of the COVID-19 pandemic and the implementation of a variety of mitigations for study conduct will be reviewed and evaluated carefully for the safety assessment. The pandemic-related protocol deviations including missed or delayed visits, missed safety-related tests, use of alternative assessment procedures for visit execution, use of alternative data collection or alternative modalities, use of rescue medications, or non-adherence to the planned course of treatment will be identified. Additional data summaries and analyses addressing the impact of the pandemic may be performed if necessary.

## 4.5.1 Study Drug Exposure

All doses of study medication are to be self-administered or administered by an individual trained in giving the injection. Study personnel may administer the injection on days of clinic visits. The overall duration of study drug exposure will be calculated using the data recorded on the eCRF as follows:

• Overall duration of study drug exposure (days) = (date of last dose – date of first dose) + 1.

The total number of doses delivered and study drug administration compliance will be calculated in two ways as follows:

- Based on missed doses in subject diary:
  - Number of doses delivered = Overall duration of study drug exposure Total number of missed doses per subject diary
  - Percent compliance (%) to study drug administration = (Number of doses delivered / Overall duration of study drug exposure) x 100%
- Based on measurement of drug remaining in pen:
  - Number of doses delivered = [(45.5 mm × Number of used pens) Sum of measurements of drug remaining in all used pens)] /1.08 mm. Here the 45.5mm is the initial measurement of unused study drug in an unused injection pen and 1.08mm is the distance the plunger travels for each 80 ug dose from the pen.
    - Note: If the measurement of drug remaining in any used pen is missing, then 100% compliance will be assumed for the treatment period for which the pen with missing measurement of drug remaining was dispensed. The number of doses taken from the pen with missing measurement of drug remaining is a value less than or equal to 30, which will be based on the number of doses taken from the pen(s) with non-missing measurement of drug remaining dispensed at the same visit as the pen with missing

measurement of drug remaining. The number of doses delivered would be the minimum of the following:

- Total doses taken from pens with non-missing measurements of drug remaining (calculated as: [45.5 mm × Number of pens with non-missing measurements of drug remaining - Sum of measurements of drug remaining from all pens with nonmissing measurements of drug remaining] /1.08 mm) + 30 × number of pens with missing measurement of drug remaining
- Duration of the treatment period for which the pen with missing measurement of drug remaining was dispensed.
- Percent compliance (%) to study drug administration = (Number of doses delivered / Overall duration of study drug exposure) x 100%

The duration of study drug exposure, duration category in months ( $\leq 1$  month,  $1 < to \leq 3$  months, 3 to  $\leq 6$  months, 6 to  $\leq 9$  months, and > 9 months), number of doses delivered, and percent compliance to study drug administration will be summarized by treatment group for the Safety, ITT, and PP populations.

To evaluate the relationship between study drug exposure and the antibody status, the duration of study drug exposure and percent compliance to study drug administration will also be summarized by antibody status (ADA-, ADA+/Nab+, ADA+/Nab-, All ADA+, and Overall) using the Antibody Population.

If a subject is shown to be <80% compliant with study drug administration using both calculations of study drug administration compliance, this subject will be considered as having a significant protocol deviation and thus excluded from the Per-Protocol Population.

Subjects' drug exposure and compliance will be carefully reviewed against the onset of the COVID-19 pandemic. Each subject's study drug exposure and compliance prior to 01 March 2020 and on or after 01 March 2020 will be calculated based on information collected from the subject diary:

- For subjects with last dose date prior to 01 March 2020 and subjects with first dose date on or after 01 March 2020, their duration of study drug exposure (days), number of doses delivered, and percent compliance to study drug administration relative to 01 March 2020 will be calculated as above based on missed doses in subject diary.
- For subjects who started taking the study drug prior to 01 March 2020 and continued on or after 01 March 2020, their duration of study drug exposure and compliance before 01 March 2020 and on or after 01 March 2020 will be calculated as follows:
  - Duration of study drug exposure relative to 01 March 2020:
    - Duration before 01 March 2020 = 29 February 2020 date of first dose + 1
    - Duration on or after 01 March 2020 = Overall duration of study drug exposure duration before 01 March 2020; where overall duration of study drug exposure = last dose date – first dose date + 1
  - The number of doses delivered relative to 01 March 2020:

- Number of doses delivered before 01 March 2020 = A {B + ([C x D] / E)}, and will be rounded to the nearest integer; where:
  - A = Duration of study drug exposure before 01 March 2020
  - B = Total number of missed doses from pens dispensed before 01 March 2020 and with scheduled return dates before or on 01 March 2020
  - C = Number of missed doses from pens dispensed during the last drug dispensing visit prior to 01 March 2020 but with scheduled return date after 01 March 2020
  - D = 01 March 2020 last drug dispensing date prior to 01 March 2020
  - E = (number of dispensed pens during the last drug dispensing visit prior to 01 March 2020 - 1) x 30.
- Number of doses delivered on or after 01 March 2020 = Number of doses delivered during whole study – number of doses delivered before 01 March 2020.
- The percent compliance (%) to study drug administration relative to 01 March 2020:
  - Percent compliance before 01 March 2020 = (Number of doses delivered before 01 March 2020 / Duration of study drug exposure before 01 March 2020) x 100%
  - Percent compliance on or after 01 March 2020 = (Number of doses delivered on or after 01 March 2020 / Duration of study drug exposure on or after 01 March 2020) x 100%.

The study drug exposure and percent compliance to study drug administration before 01 March 2020 and on or after 01 March 2020 will be summarized by treatment group respectively.

The study drug exposure and compliance will also be summarized based on subject study status during the pandemic (completed or withdrew from the study before 01 March 2020 vs ongoing on or after 01 March 2020) and by region (North America and Europe).

All study drug administration and accountability data will be listed by treatment, study site, and subject number.

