5.5. Treatment Compliance

To ensure treatment compliance, the Investigator or designee will supervise all study drug administration that occurs at the site. At each study visit, the Investigator or designee will review subject compliance with study drug administration and remind the subject of study drug dosing requirements. Subject compliance will be ascertained by 2 methods: subject diaries and measuring the residual drug in the cartridge.

Discrepancies will be discussed with the subjects, documented in the medical charts, and recorded in the eCRF as appropriate. If a subject does not take all study medication (abaloparatide-SC, placebo, calcium, and vitamin D supplements), the reason for the missed dosing is to be recorded by the subject in their diary.

If a subject demonstrates continued noncompliance of study drug dosing despite educational efforts, the Investigator should contact the Medical Monitor to discuss discontinuation of the subject from the study.

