#### 2.2 **Protocol Deviation**

A protocol deviation (PD) is any change, divergence, or departure from the study design or procedures defined in the protocol. The PD categories related to study conduct are described in the Management of Protocol Deviations/Waivers section of the Medical Management Plan. PDs are recorded by the contract research organization (ICON) in their Clinical Trial Management System (CTMS). Subjects with at least one protocol deviation will be presented in a data listing, with indicators for key and non-key PDs (as defined in Appendix 1 of the Medical Management Plan, where a key PD is a deviation requiring reporting to the Functional Lead, Medical Monitor and or Sponsor). A summary table of the key PDs identified during the study will be presented.

Significant PDs are PDs that have the potential to impact the efficacy of the treatment on the subject.

The algorithm to determine significant PDs is in Appendix A of this SAP. Subjects with at least one significant PD will be excluded from the PP population. A Per-Protocol Memo with the algorithm in Appendix A together with the programming specification ("Per Protocol Population Data Set Development") will be developed and finalized prior to database lock to detail how each of the criteria in the algorithm can be programmed in SAS. The list of subjects with significant protocol deviations identified after applying the algorithm to the unblinded SDTM data after database lock will be reviewed and approved internally at Radius in a separate memo. A summary table of reasons for exclusion from the PP population will be presented. A data listing for subjects excluded from the PP population together with the exclusion reason(s) will be presented.

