# Appendix A. Algorithm to Identify Significant Protocol Deviations that Exclude Subjects from the Per-Protocol (PP) Population

A protocol deviation is any change, divergence, or departure from the study design or procedures defined in the protocol. Significant PDs are a subset of PDs that have the potential to impact the effect of the treatment on the subject.

The below algorithm outlines the criteria for identifying significant protocol deviations. Subjects with at least one of these significant protocol deviations will be excluded from the PP population.

- A. Deviations of subject eligibility (Inclusion/Exclusion criteria) that will result in exclusion from PP population:
  - 1. Inclusion Criterion #2: A BMD T-score above the required level.
  - 2. Exclusion Criterion #2: A BMD T-score below the required limit.
  - 3. Exclusion Criterion #1: Presence of abnormalities of the lumbar spine that would prohibit assessment of spinal bone mineral density.
  - 4. Exclusion Criterion #3: Unevaluable hip BMD or subjects who have undergone bilateral hip replacement.
  - 5. Exclusion Criterion #4: Fragility fracture within the 12 months prior to signing of informed consent.
  - 6. Exclusion Criterion #5: History of severe vertebral fracture or > 2 moderate vertebral fractures.
  - 7. Exclusion Criteria #6, #8, and #10: Diseases and treatments affecting the bone strength.
  - 8. Inclusion Criterion #5: Laboratory tests affecting the bone strength
  - 9. Exclusion Criteria #18, #19, #20, #21, #22, #23, #24, #25, and #27. Prior treatment with bone acting agents within the specified time period.
- B. Deviations of study drug administration that will result in exclusion from PP population:
  - 1. The blinding of the study drug was broken during the subject's participation in this study before database lock.
  - 2. Duration of study drug exposure is less than 3 months (90 days)
  - 3. Compliance to study drug administration < 80%
- C. Deviations of efficacy measurements that will result in exclusion from PP population:
  - 1. Lumbar spine BMD is missing at baseline
  - 2. No post-baseline lumbar spine BMD measurements recorded
- D. Other significant protocol deviations
  - 1. Any protocol deviation with potential major impact on the primary efficacy endpoint will exclude a subject from the PP population. This will include subjects taking any prohibited medications during study.

Lab Parameter	Conventional Unit		SI Unit	
	Low	High	Low	High
Hematology				·

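### SAP 4.5.1 credits unmeasured pens as fully used and needs both compliance figures below 80% for Per-Protocol exclusion, so enough missing measurements can override a poor diary; Appendix A does not say which figure counts

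*SAP*

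**What the plan says.** Protocol 5.5 sets up two measures: "Subject compliance will be ascertained by 2 methods: subject diaries and measuring the residual drug in the cartridge". SAP 4.5.1 turns each into a dose count and divides it by the duration of exposure. The diary count is duration minus recorded missed doses. The pen count comes from plunger travel.

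For a used pen with no residual measurement, the note in SAP 4.5.1 makes these statements:

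- It opens with a general rule: "then 100% compliance will be assumed for the treatment period for which the pen with missing measurement of drug remaining was dispensed".
- It then limits the credit for each such pen: "The number of doses taken from the pen with missing measurement of drug remaining is a value less than or equal to 30", with the value tied to the measured pens from the same visit.
- It ends with a formula: "The number of doses delivered would be the minimum of the following", namely (a) doses from the measured pens plus 30 for each unmeasured pen, or (b) the length of the treatment period concerned.

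The same section sets the exclusion rule: "If a subject is shown to be <80% compliant with study drug administration using both calculations of study drug administration compliance", the subject has a significant deviation and is left out of the Per-Protocol population.

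SAP 2.2 points elsewhere for that decision: "The algorithm to determine significant PDs is in Appendix A of this SAP". Item B.3 there is a single line, "Compliance to study drug administration < 80" (per cent), with no mention of diary, pen, either or both. SAP 2.2 also promises a memo that "will be developed and finalized prior to database lock to detail how each of the criteria in the algorithm can be programmed in SAS".

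**The concern.** The pen measure is there to check the diary. Where the pen was not measured there is no check, yet the plan fills the gap with the most favourable value. Because exclusion needs both figures below 80%, that filled-in value can outweigh a diary that positively records more than 20% of doses missed.

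At stake are the Per-Protocol repeats of the primary and key secondary analyses (SAP 4.3.1 and 4.3.2), which are meant to support the ITT findings, and the pen-based compliance summary for the Safety, ITT and Per-Protocol populations. Missing measurements are plausible: pens are returned at clinic visits (Protocol 5.4), while home visits and home drug delivery were allowed (Protocol 5.2.1 and 6.2.1).

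The silence in B.3 is a separate weakness. It belongs to the list that SAP 2.2 names as the algorithm, and a programmer working from that list alone could exclude on either measure.

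**Working it through.** The documents state no figure that depends on this rule, so there is nothing to reproduce. The check applies the SAP formula to a worked case.

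**Inputs.** A pen delivers 30 daily doses (Protocol 5.1.1). A month is 30 days, and visits fall at Day 1 and Months 1, 3, 6, 9 and 12 (Protocol 6.2). The dispensing periods are therefore 30, 60, 90, 90 and 90 days: 360 days and 12 used pens.

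**Assumptions.** The course is complete, true compliance *c* is constant, and the diary reflects *c*. The minimum is taken within each dispensing period. The note does not say so, but comparing study-total doses with one 90-day period would cap compliance at 90/360 = 25%, which cannot be intended.

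**Formula.** With *k* unmeasured pens, pen compliance = [*c*(360 − 30*k*) + 30*k*]/360. This reaches 80% when *c* ≥ (288 − 30*k*)/(360 − 30*k*).

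| Unmeasured pens (of 12) | Lowest true compliance retained |
|---|---|
| 1 | 258/330 = 78.2% |
| 2 | 228/300 = 76.0% |
| 3 | 198/270 = 73.3% |
| 4 | 168/240 = 70.0% |
| 6 | 108/180 = 60.0% |
| 8 | 48/120 = 40.0% |
| 9 | 18/90 = 20.0% |
| 10 or more | any value |

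**Examples.**

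- *c* = 70%, 1 pen: (231 + 30)/360 = 72.5%, excluded.
- *c* = 70%, 3 pens: (189 + 90)/360 = 77.5%, excluded.
- *c* = 70%, 4 pens: (168 + 120)/360 = 80.0%, retained.
- *c* = 60%, 6 pens: (108 + 180)/360 = 80.0%, retained.
- *c* = 50%, 7 pens: (75 + 210)/360 = 79.2%, excluded; 8 pens: (60 + 240)/360 = 83.3%, retained.
- All 12 pens unmeasured: 100%, retained whatever the diary shows.

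**The note disagrees with itself.** Take a 90-day period with one of three pens unmeasured and the other two at 50%. The formula gives min(15 + 15 + 30, 90) = 60 doses, or 60/90 = 67%. The opening statement of the note gives 100%.

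The choice of reading can change who is excluded. With one unmeasured pen in each of two 90-day periods and *c* = 60%, the formula gives (0.6 × 300 + 60)/360 = 66.7% (excluded). Crediting both periods in full gives (0.6 × 180 + 180)/360 = 80.0% (retained). With one unmeasured pen in one 90-day period, full-period credit retains men from 73.3% upward, against 78.2% under the formula.

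**The case against.** The case for leaving the rule alone has several parts.

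- **Reach.** A reader might infer that any poor complier with an unmeasured pen stays in the Per-Protocol set. The documents do not support that. The rule matters only when the diary is below 80%, and then only if enough pens are unmeasured. Protocol 5.4 to 5.6 require pens to be returned, residual drug measured and inventories verified, so half or more of a man's pens going unmeasured should be uncommon. This stands.
- **Two populations.** A reader might also infer that SAP 4.5.1 and Appendix A define different Per-Protocol populations. That is too strong. B.3 is unspecified rather than contradictory, and can be read as shorthand for SAP 4.5.1. The memo due before database lock could settle it. But the memo is to implement Appendix A, which is silent on this point.
- **Two-measure rule.** Requiring two imperfect measures to agree before a post-randomisation exclusion is a legitimate prespecified choice. This stands, and the rule need not change.
- **The diary also errs upward.** An unrecorded missed dose counts as taken. True, but that does not make 100% the better substitute: a diary below 80% is a positive record of missed doses.
- **Consequence.** The primary comparison is ITT, and retaining poor compliers would be expected to dilute a Per-Protocol effect, not create one. Diary compliance is unaffected. Appendix A also excludes exposure under 90 days (B.2) and deviations with potential major impact on the primary endpoint (D.1). These limit the harm, but neither item sets the compliance calculation.

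**Conclusion.** The point holds as a minor one. An absent pen measurement is imputed favourably, and under the two-measure rule it can keep a man whose diary is below 80% in the Per-Protocol population. The size runs from almost nothing with one unmeasured pen (true compliance of about 78.2% to just under 80%, by the formula) to complete override of the diary when no pen is measured.

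These figures rest on the assumptions listed with the calculation. The documents give no missing-pen rate, so the number of men affected cannot be estimated. The note's two statements need reconciling, and B.3 needs to name the calculation. Nothing here touches the primary ITT result; the effect is confined to the supportive Per-Protocol analyses and the pen-based compliance summary.

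**What to change.** Three edits to the SAP before database lock:

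1. In 4.5.1, for any dispensing period with an unmeasured pen, replace the assumed 100% and the 30-dose credit with the diary dose count for that period. If no pen is measurable, use the diary alone. This also removes the note's internal disagreement.
2. Keep the prespecified rule that both calculations must be below 80%.
3. Restate that rule in the same words in Appendix A B.3, and carry it into the Per-Protocol memo.

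Under the assumptions above, a man whose true compliance is below 80% would then be excluded however many pens are unmeasured. No new data are needed: the split at 01 March 2020 in SAP 4.5.1 already uses missed doses by dispensing visit. The cost is SAP wording and programming, and a few more men may leave the Per-Protocol set.

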#### 3.12 Visit Windows

In general, the nominal visit will be used for the safety and efficacy data summaries and analyses.

During the COVID-19 pandemic, if a subject's DXA and/or QCT assessment cannot be performed during the protocol specified visit windows, the site will contact the study Medical Monitor and the subject will be allowed to make up the visits within an allowed time period. The allowable time period for collection of DXA and QCT assessments are shown in Table 3, where the ideal visit date is defined as the date that represents the ideal number of days from the date of first dose of study drug to the nominal visit.

Table 3:         Allowable Time Period for Collection of DXA and QCT Assessment
---

Visit	Ideal Visit Day	BMD or vBMD Assessment
Month 3	90	Up to 30 days after ideal visit day
Month 6	180	Up to 90 days after ideal visit day
Month 12	360	Up to 30 days after ideal visit day

Due to the expanded time periods for collection of efficacy assessments, analysis visit windows are defined below for the analyses of BMD, vBMD, and serum markers of bone metabolism (PINP and CTX) data to determine the assessment that will be used for a given study visit.

Table 4: Analysis V	Visit Windows	for BMD.	, vBMD, s	s-PINP and	I s-CTX.
---------------------	---------------	----------	-----------	------------	----------

Visit / Month	Allowable days from first dose of study drug			
	BMD lumbar spine, total hip and femoral neck, BMD Wrist	s-PINP, s-CTX	vBMD	
Visit 3 / Baseline	≤1	$\leq 1$	≤ 1	
Visit 4 / Month 1		2—60		
Visit 5 / Month 3	2—120	61—120		
Visit 6 / Month 6	121—270	121—270		
Visit 7 / Month 9				
Visit 8 / Month 12	≥ 271	≥271	≥2	

*Study BA058-05-019 SAP* 

It is possible that more than 1 assessment for a parameter may be obtained within the same analysis visit window. In such circumstances, the assessment with the date closest to the ideal visit day will be used. In the event that 2 assessments are equidistant to the ideal visit day, the later of the assessments will be used.

The analysis visit window convention will not be applied to the data listings. The data listings will display all data as collected with the corresponding nominal visit.

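### The compliance split at 01 March 2020 can show a false change for a man who misses doses and stops early, or doses late, in the dispensing interval around that date

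*SAP*

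**What the plan says.** SAP section 4.5.1 calculates exposure and diary compliance separately before, and on or after, 01 March 2020. The split formula is for one group: "For subjects who started taking the study drug prior to 01 March 2020 and continued on or after 01 March 2020".

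Doses delivered before the cut are given as "A {B + ([C x D] / E)}, and will be rounded to the nearest integer". The gap after the first A is a minus sign lost from the text I worked from, not a fault in the plan. The terms are:

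- "A = Duration of study drug exposure before 01 March 2020", counted from actual dates.
- "B = Total number of missed doses from pens dispensed before 01 March 2020 and with scheduled return dates before or on 01 March 2020".
- C: missed doses from the last dispensing before the cut, "but with scheduled return date after 01 March 2020".
- D: days from that dispensing to 01 March 2020, also from actual dates.
- "E = (number of dispensed pens during the last drug dispensing visit prior to 01 March 2020 - 1) x 30".

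Doses on or after the cut are whole-study doses minus doses before the cut. Each count is divided by the actual exposure days on its side, and both percentages are summarized by treatment group.

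**The concern.** C accumulates over the days a man really doses from that dispensing. E is the number of days the pens were nominally meant to cover, and it uses neither his last-dose date nor his actual return date. D/E is therefore the right share only when those two lengths agree. The sort into B or C has a similar weakness. An interval scheduled to end by 01 March but actually ending later has all its missed doses charged to the earlier period.

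Because the later period is found by subtraction, any error before the cut reappears after it with the opposite sign, sometimes over far fewer days. The purpose of the table is to show whether compliance changed when the pandemic began, and the rule can produce such a change in a man whose behaviour was constant.

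**Working it through.** The documents state no result for this split, so there is no figure to reproduce. The check is to give the formula a man whose compliance never changes and see whether both sides agree.

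**Algebra.** Let m be a constant missed-dose rate and L the days actually dosed from the straddling dispensing. Then C = mL. The SAP places mL × D/E of these missed doses before the cut; the correct number is mD. The error is mD(L/E − 1), which is zero only if L = E or m = 0. L < E moves missed doses to after the cut, and L > E moves them to before it.

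**Inputs.** The formula and its rounding come from SAP 4.5.1. The 30-day pen life is in protocol section 5.4. Pens per visit are not stated; protocol 5.2.1 refers to the Pharmacy Manual. I assume four pens (one spare) for a 90-day interval, so E = 90. The values of m, D and L, and the calendar dates below, are illustrative.

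**Whole-number cases.** m = 20%, 90 earlier days (so 18 earlier missed doses), E = 90, true compliance 80% throughout:

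| Case | D | L | Before | After |
|---|---|---|---|---|
| On time, then 180 more days | 30 | 90 | 96/120 = 80.0% | 192/240 = 80.0% |
| Stops early | 30 | 40 | 99/120 = 82.5% | 5/10 = 50.0% |
| Stops early, but later | 30 | 60 | 98/120 = 81.7% | 22/30 = 73.3% |
| Returns late, no later dosing | 60 | 120 | 116/150 = 77.3% | 52/60 = 86.7% |
| Returns late, then 150 more days | 60 | 120 | 116/150 = 77.3% | 172/210 = 81.9% |
| Scheduled return before the cut, actual return after it, no later dosing | 95 | 120 | 143/185 = 77.3% | 25/25 = 100.0% |

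The second row in full: C = 0.20 × 40 = 8. Missed before = 18 + 8 × 30/90 = 20.67. Doses before = 120 − 20.67 = 99.33, rounded to 99. Whole-study doses = 130 − 26 = 104, which leaves 5 doses over 10 days. In the last row, B takes all 18 + 24 = 42 missed doses, so 185 − 42 = 143.

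**Calendar illustrations.** These use expected, hence fractional, missed doses and the SAP's rounding.

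1. True 75%. First dose 03 November 2019, four pens dispensed 01 February 2020, last dose 20 March 2020. A = 119, B = 0.25 × 90 = 22.5, L = 49, C = 12.25, D = 29. Missed before = 22.5 + 12.25 × 29/90 = 26.45. Doses before = 92.55, rounded to 93, so 93/119 = 78.2%. Whole-study doses = 139 − 34.75 = 104.25. After = 11.25/20, about 56.2%.
2. True 85%. First dose 15 March 2019, four pens dispensed 10 December 2019, last dose 08 April 2020, 30 days after the interval's nominal end. A = 352, B = 0.15 × 270 = 40.5, L = 121, C = 18.15, D = 82. Missed before = 40.5 + 18.15 × 82/90 = 57.04. Doses before = 294.96, rounded to 295, so 295/352 = 83.8%. Whole-study doses = 391 − 58.65 = 332.35. After = 37.35/39 = 95.8%.

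**Where nothing goes wrong.** There is no false change for a man with no missed doses, or for one who stops in a later interval (D = 30, L = 90, then 40 days: 96/120 and 80/100, both 80.0%). A five-day delay (D = 45, L = 95, 180 further days) disappears in the rounding.

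**Range on the pen count.** With three pens for a 90-day interval (E = 60), the man in the second row shows 98/120 = 81.7% and 6/10 = 60.0%. Even the on-time man is then misread: 93/120 = 77.5% before and 195/240 = 81.2% after.

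**The case against.** The strongest reply is that little depends on this and that the disturbed cases are narrow. Much of that stands. The error needs missed doses together with an early stop, or a material overrun, in the one interval that spans 01 March 2020 or was scheduled to end just before it. The large fall in the first calendar illustration owes much to only 20 days after the cut. The second takes dosing past the nominal 360-day treatment period, and one day past four pens' 120-day supply; the documents do not say that dosing would be extended in this way. The table rows for a mid-study late return avoid the first difficulty and show a smaller rise.

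SAP section 3.12 says that "the subject will be allowed to make up the visits within an allowed time period", and its Table 3 gives 30 to 90 days. A reader might infer that pens may come back that late. The documents do not support this: Table 3 concerns DXA and QCT collection, the 90 days applies to Month 6 only, and protocol sections 5.2.1 and 6.2.1 allow home delivery of drug, so a late scan need not mean a late resupply. A reader might also point to E = 0 after a single-pen dispensing, or to an E inflated by a replacement pen. Both are hypothetical without the pen plan, and the second arises only if the extra pen is issued at that same visit.

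The SAP also captures disruption elsewhere, through the COVID-19 Impact Log (section 4.1) and the listings of administration and accountability data (section 4.5.1). None of this makes the stated formula correct. Early stopping is foreseen (the sample size allows 10% drop-out), and the Impact Log has categories for discontinuation and out-of-window visits.

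**Conclusion.** The point holds in limited form. The pro-rating and the B/C sort mix actual dates with nominal supply and scheduled dates. A man with constant compliance below 100% can then appear to fall after 01 March 2020 if he stops early in the straddling interval, or to rise if he keeps dosing from it past E days or returns late. In the cases worked with four pens, the gap between the two percentages runs from none to about 32 points (82.5% against 50.0%), and it shrinks when many days of dosing follow the cut.

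A reader might infer that the whole table is uninterpretable, or that it fails for every man whose treatment the pandemic disrupted. Neither follows. Disruption in later intervals does no harm, and the number of men affected is not in the documents, so the effect on the group summaries cannot be sized. Nor does it reach the main results: whole-study compliance, the below-80% Per-Protocol rule and the primary analysis do not use the split. This is a minor correction to a descriptive summary. The figures rest on the assumed pen count, missed-dose rates and interval lengths.

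**What to change.** In SAP section 4.5.1:

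- Define E as the actual days dosed on the last dispensing before 01 March 2020, counted from the dispensing date through the last dose date, or up to but excluding the next dispensing date if that is earlier. This counts days in the same way as D.
- Assign missed doses to B if that interval actually ended before 01 March 2020, and to C if it spanned the date.
- If the diary dates each missed dose, which the documents do not establish, count missed doses directly on each side and drop the pro-rating.

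With the first two changes, every row of the table returns 80.0% on both sides. In the second row, for example, E = 40 gives 18 + 8 × 30/40 = 24 missed before, so 96/120 and 8/10. In the fractional illustrations only the rounding remains.

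The cost is a few lines of text and code plus one further input. Section 4.5.1 uses only scheduled return dates, so actual dispensing and return dates must be drawn from the accountability records. Pro-rating would still assume that missed doses are spread evenly within the interval, so a real change on 01 March inside it would be smoothed; only the direct count avoids that.
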